16.2.2.5.3. Change From Baseline to Week 78 in ADCS-ADL-MCI

The population will be subjects in the ITT population. An MMRM model will be used as the primary analysis to analyze change from baseline ADCS-ADL-MCI using fixed effects of treatment, time, treatment-by-time interaction, baseline ADCS-ADL-MCI, baseline ADCS-ADL-MCI by time interaction, baseline MMSE, AD symptomatic medication use at baseline, region, and laboratory ApoE ϵ 4 status.

16.2.2.6. Tertiary Endpoints Analysis

16.2.2.6.1. Placebo-Controlled Period

Where appropriate, an MMRM model will be used as the primary analysis to analyze change from baseline using fixed effects of treatment, time, treatment by time interaction, baseline value, baseline value by time interaction, baseline MMSE, AD symptomatic medication use at baseline, region, and laboratory ApoE ϵ 4 status.

Otherwise, an analysis of covariance may be used to analyze these exploratory endpoints or descriptive summary statistics may be presented.

CONFIDENTIAL

The information contained herein may not be used, disclosed, or published without the written consent of Biogen MA Inc.

16.2.2.6.2. Long-Term Extension Period

The endpoints for the LTE period are change from baseline over the placebo-controlled and LTE periods of the study. Analyses will be presented by treatment group in the LTE period using the placebo-controlled period baseline. Details of the analyses will be prespecified in the statistical analysis plan (SAP).

16.3. Pharmacokinetics

16.3.1. Analysis Population

The population for PK analysis is defined as all subjects who were randomized, were dosed with study treatment, and had at least 1 measurable aducanumab concentration in serum.

16.3.2. Method of Analysis

The serum concentrations and PK parameters of aducanumab will be summarized descriptively.

16.4. Additional Exploratory Analyses

16.5. Safety

16.5.1. Analysis Population

The safety population is defined as all subjects who were randomized and received at least 1 dose of study treatment (including placebo and aducanumab).

16.5.2. Methods of Analysis

All AEs, laboratory data, ECG, neurological and physical examinations and vital signs will be evaluated for safety.

16.5.2.1. Adverse Events

Only treatment-emergent adverse events (TEAEs) will be presented in the summary tables. Treatment emergent is defined as having an onset date that is on or after the start of study treatment, or as worsening after the start of study treatment.

Incidence of TEAEs will be summarized by treatment groups, overall, by severity, and by relationship to study treatment for the placebo-controlled period and up to 5 years of LTE period. The summary tables will include incidence estimates for overall system organ class as well as for preferred terms within each system organ class. AEs will be coded using the Medical Dictionary for Regulatory Activities (MedDRA).

CONFIDENTIAL

The information contained herein may not be used, disclosed, or published without the written consent of Biogen MA Inc.

16.5.2.2. Clinical Laboratory Results

Laboratory data will be summarized using shift tables. Shifts from baseline to high/low status for hematology and blood chemistry parameters, and shifts from baseline to high/positive status for urinalysis will be presented. In addition, the shift from baseline to the maximum post-baseline value and the shift from baseline to the minimum post-baseline status will be presented for each laboratory test by treatment group. Also, summaries of laboratory values categorized based on common toxicity criteria grade will be created. Summary statistics for actual values and change from baseline will also be presented for quantitative laboratory data.

16.5.2.3. Vital Signs

The analysis of vital signs will focus on clinically relevant abnormalities.

16.5.2.4. ECG

The number and percentage of subjects with shifts to categorical values (abnormal not AE, or abnormal AE) will be summarized by treatment group.

16.5.2.5. Columbia Suicide Severity Rating Scale

The C-SSRS data will be summarized by treatment group.

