Study Week	Placebo-Controlled Period ¹							UV for ARIA ³
	12	24	26	48	50	72	78 (EOT) ²	
Study Day	85 ± 3	169 ± 3	183 ± 3	337 ± 3	351 ± 3	505 ± 3	547 ± 3	
Informed Consent							X ⁴	
Body Weight	X	X		X		X		
Eligibility Criteria							X ⁴	
Physical Examination	X	X		X		X	X	
Neurological Examination	X	X		X		X	X	
12-lead Paper ECG		X		X		X	X	
Vital Signs	X	X		X		X		
Hematology, Blood Chemistry and Urinalysis		X		X		X	X	
PBMC Collection								X ⁵
Aducanumab Concentration								X ⁶
Brain MRI ⁷							X	X
Amyloid PET ⁸			X				X	
CDR			X		X		X	
MMSE			X		X		X	
ADAS-Cog 13			X		X		X	
ADCS-ADL-MCI			X		X		X	

CONFIDENTIAL

The information contained herein may not be used, disclosed, or published without the written consent of Biogen MA Inc.

Study Week	Placebo-Controlled Period ¹							UV for ARIA ¹
	12	24	26	48	50	72	78 (EOT) ²	
Study Day	85 ± 3	169 ± 3	183 ± 3	337 ± 3	351 ± 3	505 ± 3	547 ± 3	
NPI-10			X		X		X	
EQ-5D (SR)			X		X		X	
EQ-5D (IR-S)			X		X		X	
mPDQ-20			X		X		X	
MOCA								X
C-SSRS			X				X	
AE Reporting	Monitor and record continuously throughout the study							
Concomitant Therapy and Procedures	Monitor and record continuously throughout the study							
SAE Reporting	Monitor and record continuously throughout the study							

AD = Alzheimer's disease; AE = adverse event; ADAS-Cog 13 = Alzheimer's Disease Assessment Scale Cognitive Subscale (13 items); ADCS-ADL-MCI = Alzheimer's Disease Cooperative Study Activities of Daily Living Inventory (Mild Cognitive Impairment version); ARIA = amyloid-related imaging abnormalities; ARIA-E = amyloid-related imaging abnormality-edema; ARIA-H = amyloid-related imaging abnormality hemorrhage or superficial siderosis; [REDACTED]; CDR = Clinical Dementia Rating scale; CSF = cerebrospinal fluid; C-SSRS = Columbia Suicide Severity Rating Scale; ECG = electrocardiogram; EOT = end of treatment; [REDACTED]; EQ-5D (IR-S) = EQ-5D, informant reported on subject; EQ-5D (SR) = EQ-5D, subject self-reported; FU = follow-up; LTE = long-term extension; MMSE = Mini Mental State Examination; mPDQ-20 = modified Perceived Deficits Questionnaire-20; MOCA = Montreal Cognitive Assessment; MRI = magnetic resonance imaging; NPI-10 = Neuropsychiatric Inventory-10; PBMC = peripheral blood mononuclear cells; PET = positron emission tomography; PK = pharmacokinetic; RNA = ribonucleic acid; SAE = serious adverse event; SoE = schedule of events; UV = unscheduled visit.

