¹ Subjects who discontinue study treatment prematurely during the placebo-controlled period are to remain in the study, attend a FU Visit 18 weeks after their final dose as listed in Table 2 and Table 3, and immediately continue protocol-required tests and assessments at a subset of the clinic visits (see Table 10, and Table 11) until the end of the study per the schedule of events. (It is possible that a clinic visit will occur before the FU Visit.) If the FU Visit will occur within 2 weeks of a scheduled clinic visit, then the FU Visit can be combined with the scheduled visit and all assessments required for both visits performed at this single visit. If the subject who discontinued treatment but remained in the study chooses to enroll in the LTE period, he or she will follow the SoE in Table 11.

CONFIDENTIAL

The information contained herein may not be used, disclosed, or published without the written consent of Biogen MA Inc.

- ² Subjects who withdraw from study prematurely are to return to the site for an EOT Visit; for such subjects, efficacy assessments specified at the EOT Visit are not required if the subject discontinues treatment within 3 months of the previous efficacy assessment visit and no significant changes in cognitive status are suspected by the Investigator. The site should notify the Sponsor in such cases.
- ³ For the frequency of required brain MRI and MOCA assessments, and PK, biomarker, and PBMC sample collection for subjects who develop ARIA-E and/or ARIA-H, see Section 7.2.1.1 to Section 7.2.1.5. This includes PK, biomarker, and PBMC sample collection at the first unscheduled visit for ARIA monitoring per episode only. For the frequency of brain MRI and MOCA assessments following resolution of ARIA and resumption of dosing, see Section 7.2.1.6. For management of recurrent ARIA, see Section 7.2.1.7.
- ⁴ Only for subjects entering the long-term extension period.
- ⁵ Sample may be collected within ± 2 days of the MRI visit at the same time as sample collection for aducanumab concentration.
- ⁶ One sample will be collected within ± 2 days of the MRI visit. Exact collection date and time will be captured for all PK blood samples on a specified case report form.
- ⁷ Arterial spin labeling MRI and task-free functional MRI will be performed only at a subset of sites.
- ⁸ Only for subjects who participate in the amyloid PET substudy. Amyloid PET may be scheduled within a window of ± 7 days.

CONFIDENTIAL

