The information contained herein may not be used, disclosed, or published without the written consent of Biogen MA Inc.

Table 11: Subjects Who Discontinue Study Treatment but Remain in the Study – Long-Term Extension Period

Study Week	LTE Period ¹															UV for ARIA ¹
	92	104	106	128	134	152	162	176	182	208	232	260	284	312	338 (EOT) ²	
Study Day	645 ± 5	729 ± 5	743 ± 5	897 ± 5	939 ± 5	1065 ± 5	1135 ± 5	1233 ± 5	1275 ± 5	1457 ± 5	1625 ± 5	1821 ± 5	1989 ± 5	2185 ± 5	2367 ± 5	
Body Weight	X	X		X		X		X	X	X	X	X	X	X	X	
Physical Examination	X	X		X		X		X	X	X	X	X	X	X	X	
Neurological Examination	X	X		X		X		X	X	X	X	X	X	X	X	
12-lead Paper ECG		X		X		X		X								
Vital Signs	X	X		X		X		X	X	X	X	X	X	X	X	
Hematology, Blood Chemistry and Urinalysis		X		X		X		X			X		X			
PRMC Collection																X ³
Aducanumab Concentration																X ⁴
Brain MRI ⁷					X				X		X		X		X ⁷	X
Amyloid PET ⁸									X			X			X	
CDR			X		X		X		X		X		X		X	
MMSE			X		X		X		X		X		X		X	
ADAS-Cog 13			X		X		X		X		X		X		X	
ADCS-ADL-MCI ¹			X		X		X		X		X		X		X	
NPI-10			X		X		X		X						X ⁴	

CONFIDENTIAL

The information contained herein may not be used, disclosed, or published without the written consent of Biogen MA Inc.

Study Week	LTE Period ¹															UV for ARIA ³
	92	104	106	128	134	152	162	176	182	208	232	260	284	312	338 (EOT) ²	
Study Day	645 ± 5	729 ± 5	743 ± 5	897 ± 5	939 ± 5	1065 ± 5	1135 ± 5	1233 ± 5	1275 ± 5	1457 ± 5	1625 ± 5	1821 ± 5	1989 ± 5	2185 ± 5	2367 ± 5	
EQ-5D-(IR-S)			X		X		X		X		X		X		X	
MOCA																X
C-SSRS			X		X		X		X		X		X		X	
AE Reporting	Monitor and record continuously throughout the study															
Concomitant Therapy and Procedures	Monitor and record continuously throughout the study															
SAE Reporting	Monitor and record continuously throughout the study															

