In the most recent interim analysis (25 May 2017), the incidence of ARIA has been observed to be both dose- and ApoE ϵ 4 carriage-dependent, especially at the highest doses when administered as a fixed dose. ARIA-E was radiographically monitored by magnetic resonance imaging (MRI) and typically observed early in treatment (between 2 to 5 doses). In most cases, ARIA-E resolved 4 to 12 weeks after onset and ARIA-H was typically stable 2 to 4 weeks after onset. In the placebo-controlled period, the incidence of ARIA-E appeared to be lower in the group receiving titration to 10 mg/kg (comprising ApoE ϵ 4 carriers only; 8/23 [35%]) than in carriers in the 6 mg/kg and 10 mg/kg fixed-dose groups (9/21 [43%] and 11/20 [55%], respectively). Of note, among the subjects receiving titration to 10 mg/kg who had ARIA-E, the abnormalities were observed at the 3 and 6 mg/kg dose levels, before they reached

CONFIDENTIAL

The information contained herein may not be used, disclosed, or published without the written consent of Biogen MA Inc.

10 mg/kg. Also, 13 (of 23, 57%) subjects in the titration arm have been titrated to 10 mg/kg, and of these, 12 continued treatment and received at least 17 doses of 10 mg/kg; none of these subjects experienced ARIA-E or ARIA-H. Furthermore, ARIA-E events when they occurred (in the titration group) have been either asymptomatic or associated with mild symptoms that resolved, and most subjects who had ARIA-E continued treatment (6/8; 75%) compared with only 36% (4/11) of carriers in the fixed-dose 10 mg/kg arm (refer to the IB for details on events of ARIA). In the LTE period, the incidence of ARIA-E in ApoE ϵ 4 carriers who were titrated up to 6 mg/kg (2 doses of 3 mg/kg, then 6 mg/kg) was 23% (3/13), with an overall rate of 16% (3/19) as no ApoE ϵ 4 non-carriers (0/6) experienced ARIA-E.

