10. DISCONTINUATION OF STUDY TREATMENT AND/OR WITHDRAWAL OF SUBJECTS FROM THE STUDY

10.1. Discontinuation of Study Treatment

A subject *must* permanently discontinue study treatment for any of the following reasons:

- The subject develops any of the following:
 - ARIA-E accompanied by serious clinical symptoms except for “other medically important event” as defined in [Table 13](#).
 - Symptomatic ARIA-H (microhemorrhages) with serious clinical symptoms except for “other medically important event” as defined in [Table 14](#).
 - Symptomatic ARIA-H (superficial siderosis) with or serious clinical symptoms except for “other medically important event” as defined in [Table 15](#).
 - ARIA-H with ≥ 10 microhemorrhages and/or >2 focal areas of superficial siderosis.
 - Any new incident macrohemorrhage (defined as >1 cm in diameter on T2* sequence).

See Section 7.2.1 for full details regarding discontinuation and dose reduction due to ARIA-E or ARIA-H.

- The subject becomes pregnant. Study treatment must be discontinued immediately and pregnancy must be reported according to the instructions in Section 15.4.1.
- The subject withdraws consent to continue study treatment.
- The subject experiences a medical emergency that necessitates permanent discontinuation of study treatment or unblinding of the subject's treatment assignment.
- The subject experiences an AE that does not resolve or requires continued treatment that meets exclusionary criteria (see Section 11.5.1.2).
- The subject experiences a severe infusion reaction.
- At the discretion of the Investigator for medical reasons.
- At the discretion of the Investigator or Sponsor for noncompliance.

The reason for discontinuation of study treatment must be recorded in the subject's case report form (CRF).

A subject who discontinues treatment is to remain in the study, attend a FU Visit 18 weeks after the final dose, and immediately continue protocol-required tests and assessments at a subset of the clinic visits (see [Table 10](#) and [Table 11](#)) until the end of the study per the schedule of events or until the subject withdraws consent.

CONFIDENTIAL

The information contained herein may not be used, disclosed, or published without the written consent of
Biogen MA Inc.

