14.1. Clinical Safety Assessments

The following clinical assessments will be performed to evaluate the safety profile of aducanumab:

- AE and SAE monitoring.
- Physical examination, including height and weight.
- Neurological examination.
- Vital signs (body temperature, heart rate, SBP, DBP, and respiratory rate).
- 12-lead ECG.
- Brain MRI.
- Concomitant medication, therapy, and procedure monitoring.
- MOCA (for ARIA monitoring and management).
- Columbia Suicide Severity Rating Scale (C-SSRS).

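### Subjects who permanently stop treatment before Week 52 lose the mid-period C-SSRS, leaving a 52-week gap in the placebo-controlled period that one tick in Table 10 would close

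*Protocol*

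**What the plan says.** Section 14.1 lists the C-SSRS among the clinical safety assessments. Section 16.5.2.5 gives its whole analysis in one sentence: "The C-SSRS data will be summarized by treatment group".

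The timing is in Section 4.2 and depends on treatment status:

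- **On treatment.** Table 1 has the C-SSRS on Day 1 and at Week 26. Table 2 has it at Weeks 52 and 78, with nothing in the follow-up column. Week 52 is a dosing visit.
- **Treatment permanently stopped, still in the study.** Table 10 has visits at Weeks 12, 24, 26, 48, 50, 72 and 78, plus unscheduled visits for ARIA. The C-SSRS is ticked at Weeks 26 and 78 only.

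Section 10.1 sends discontinued subjects to this second schedule: "A subject who discontinues treatment is to remain in the study, attend a FU Visit 18 weeks after the final dose", and then continue at a subset of visits. The first footnote to Table 10 says that they "attend a FU Visit 18 weeks after their final dose as listed in Table 2 and Table 3". Neither table has the C-SSRS at that visit.

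For adverse events, serious adverse events and concomitant therapy, Table 10 keeps the instruction "Monitor and record continuously throughout the study".

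**The concern.** The number and spacing of C-SSRS assessments depend on whether the subject is still on treatment, yet the results are to be compared by randomized group. If one arm has more permanent discontinuation before Week 52, that arm is asked the structured suicidality questions less often in the only period with a concurrent placebo control.

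There is some reason to expect a difference. Section 5.1.2 reports from the earlier multiple-dose study that "the incidence of ARIA has been observed to be both dose- and ApoE" ε4 carriage-dependent, and Section 10.1 makes certain ARIA findings grounds for permanent discontinuation.

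The analysis plan cannot repair this, because an assessment that was never made cannot be recovered later. The remedy has to be in the protocol's schedule.

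**Working it through.** The plan states no figure on this point, so there is none to reproduce. The check compares the schedules and takes intervals from the study days printed in the tables: Week 26 = Day 183, Week 50 = Day 351, Week 52 = Day 365, Week 78 = Day 547.

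**Column alignment.** The CDR rows in the same tables fall at Weeks 50 and 78 (Table 2) and at Weeks 26, 50 and 78 (Table 10), as expected. The C-SSRS ticks can therefore be read against the week headers with confidence.

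**Intervals after Week 26:**

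| Schedule | Calculation | Longest gap | Post-baseline assessments |
|---|---|---|---|
| On treatment | (365 − 183)/7 = 26, then (547 − 365)/7 = 26 | 26 weeks | 3 |
| Off treatment, Table 10 | (547 − 183)/7 = 52 | 52 weeks | 2 |
| Table 10 with Week 50 added | (351 − 183)/7 = 24, then (547 − 351)/7 = 28 | 28 weeks | 3 |

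With the ±3-day windows, the off-treatment gap runs from (544 − 186)/7 = 51.1 to (550 − 180)/7 = 52.9 weeks.

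**Who is affected.** Weeks 26 and 78 are common to both schedules. A subject who stops at any time before Week 52, including before Week 26, goes from Week 26 to Week 78 without a C-SSRS. A subject who stops after Week 52 already has that assessment and loses nothing.

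**Long-term extension.** Off treatment, Table 11 has the C-SSRS at Weeks 106, 134, 162, 182, 232, 284 and 338. Tables 4, 5, 7, 8 and 9 give the same weeks on treatment. The mismatch is confined to the placebo-controlled period.

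**Size, under assumption.** The protocol gives no rate of stopping treatment before Week 52 while staying in the study. Call that share of an arm *p*. The number affected in an arm of 535 (Section 16.8) is 535 × *p*:

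- *p* = 5%: 26.75, about 27 subjects
- *p* = 10%: 53.5, about 54
- *p* = 20%: 107
- *p* = 30%: 160.5, about 161

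If all subjects attend to Week 78, an arm has 3 − *p* scheduled post-baseline assessments per subject on average. Two arms whose *p* differs by 10 percentage points would differ by 0.10 of an assessment out of 3, or about 3%. Averaged over an arm the imbalance is small; for each affected subject the lost year is the larger matter.

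**The case against.** The strongest reply is that Table 10 is deliberately a reduced schedule, not a contradiction. It thins other safety assessments more: scheduled post-baseline brain MRI falls from seven visits in Table 3 to Week 78, apart from the follow-up visit and unscheduled ARIA visits. Week 52 is a dosing visit and drops out with the other dosing visits. In the extension, the C-SSRS happens to fall on visits that Table 11 retains, so the match there may come from the same rule. This stands as far as intent goes: the documents do not show that the omission was an oversight. It does not explain why the assessment was not moved to Week 50, where Table 10 already brings these subjects in for the clinical scales.

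A reader might go further and infer that a safety endpoint is under-ascertained in the active arms and that the drug is therefore made to look safer. The documents do not support that reading:

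- The C-SSRS is a safety assessment, but it is not among the endpoints in Section 6.3.2 or 6.5.2. The incidence of adverse and serious adverse events is an endpoint, and both are recorded continuously off treatment.
- No stopping rate by arm is given. Under Section 7.2.1 many ARIA cases lead to continued or suspended dosing, and suspended subjects keep all scheduled visits, including Week 52. In the earlier study's titration group, 6 of 8 subjects with ARIA-E continued treatment (Section 5.1.2).
- The protocol does not state the C-SSRS recall period. If the Week 78 assessment covers the time since the last one, events in the gap are still collected, only later. The effect also depends on whether results are tabulated by visit or as any post-baseline event, which is for the analysis plan.
- The 30% in Section 16.8 is a sample-size drop-out rate, not a rate of stopping treatment while staying in the study. Subjects who withdraw return for an end-of-treatment visit and do not follow Table 10, so shares built on that 30% do not measure this problem.

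**Conclusion.** The schedule difference is real. A subject who permanently stops treatment before Week 52 and stays in the study has no scheduled C-SSRS for 52 weeks, against 26 weeks on treatment, and has two post-baseline assessments instead of three. The follow-up visit does not fill the gap.

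The consequence for the comparison by group is conditional. Ascertainment is unequal only to the extent that stopping before Week 52 differs by arm, which is plausible but not quantified in the protocol. Continuous adverse event recording limits the loss to structured solicitation. This is a cheap improvement to the schedule and does not show that the safety evidence is biased.

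**What to change.** In Table 10, add the C-SSRS to the existing Week 50 column. In the summary by treatment group, treat it as the same analysis visit as the on-treatment Week 52 assessment; the nominal dates are 365 − 351 = 14 days apart. A footnote should cover a subject who stops between Weeks 50 and 52. That subject would have attended Week 50 under Table 2, which has no C-SSRS there, and could otherwise miss both.

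No new visit is needed. The cost is one table entry, one footnote and a few minutes per discontinued subject. In return, discontinued subjects have the same number of post-baseline assessments as those on treatment, and their longest gap falls from 52 to 28 weeks. If the sponsor prefers to leave Table 10 as it is, the protocol should give the reason, and the summary should report how many subjects in each arm were assessed at each visit.

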16.6. Immunogenicity Data

16.6.1. Analysis Population

The analysis population for immunogenicity is defined as all subjects in the safety population who have at least 1 post-dose sample evaluated for immunogenicity.

16.6.2. Methods of Analysis

Anti-aducanumab serum antibodies will be summarized using shift tables.

16.7. Interim Analyses

16.7.1. Interim Futility Analysis

An interim analysis for futility of the primary endpoint will occur after approximately 50% of the subjects have completed the Week 78 Visit (or discontinued). In order to maintain the treatment blind, an independent group external to Biogen that will not be involved in the conduct of the study after unblinding will perform the interim futility analysis. This independent group will present the unblinded interim analysis to the IDMC. The IDMC may recommend terminating the study for futility if it is evident that the efficacy of aducanumab is unlikely to be achieved.

The futility criteria will be discussed in detail in the SAP.

CONFIDENTIAL

The information contained herein may not be used, disclosed, or published without the written consent of Biogen MA Inc.

